13. STATISTICAL CONSIDERATIONS

13.1 Study Design and Study Endpoint Summary

This protocol will be performed at M.D. Anderson, with a safety lead-in study to evaluate the safety, tolerability and feasibility of SBRT plus M7824 prior to initiation of the phase 2. The primary outcome for this study is the progression free survival (PFS) rate.

This is a phase I/II, open label, single arm study to evaluate M7824 plus SBRT in patients with locoregional recurrent HNSCC after prior head and neck therapy that are not good candidates for salvage surgery (Figure 1). Patients must have evaluable disease by RECIST or RECIST 1:1 and a performance status ECOG 0-2. Time elapsed from prior radiotherapy must be at least 6 months.

13.2 Safety Lead-in

The Dose limiting toxicity (DLT) window for the combination of SBRT and M7824 in patients with recurrent HNSCC is from first M7824 administration (D1) until 14 days post SBRT (D28).

Patients will be administered 12 cycles of M7824 1200 mg intravenously every 2 weeks (Q2W), starting 2 weeks prior to the first fraction of SBRT until disease progression, intolerance, or consent withdrawal for up to 1 year. A cohort of 8 patients will be enrolled in the lead-in phase to assess safety and toxicity. More than 2 DLTs in 8 evaluable patients will be considered unacceptable.

With a cohort of 8 patients, the probability of the combination M7824 plus SBRT will be considered too toxic with a probability of 0.86 if the DLT rate is 50%. If the DLT rate is 0.20, the probability that the therapy will be deemed safe is 80%.

The phase 2 trial will proceed based upon the DLT data from the first 8 patients. Data from all patients will be evaluated when available.

This study will be monitored by the MD Anderson IND Office and a protocol-specific monitoring plan will be followed.

Bayesian toxicity monitoring will be applied to evaluate the safety profile of the treatment in the first 20 patients (including both Phase I and Phase II parts of the study). The first time of the toxicity monitoring will be in the cohort of the first 8 patients as described earlier. The treatment is considered too toxic if Probability (DLT rate > 0.3) > 0.6 . Based on the criteria and a prior distribution of the probability of toxicity as beta (0.3, 0.7), the patient enrollment will be halted if the numbers of observed DLTs exceed the following stopping rules:

at least 3 in 8, 4 in 9-11, 5 in 12-14, 6 in 15-17, and 7 in 18-20 patients.

If the stopping boundary is crossed, the results will be reported to the principal investigators and the study supporting company EMD Serono. The PI and supporting company EMD Serono will review this data to determine if the study design will need to be adjusted. By applying this rule, the following table shows the operating characteristics of the Bayesian toxicity monitoring rule. The results were obtained from the Bayesian toxicity monitoring program version 2.1.1 at <http://ibl.mdanderson.org/BTM/>.

Scenario	Prob.Of.Tox	Prob.Early.Stop	Prob.Declare.Tox	Avg.N.Patients
1	0.1	0.045	0.045	20.444
2	0.2	0.272	0.279	17.832
3	0.3	0.611	0.631	13.986
4	0.4	0.866	0.883	10.754
5	0.5	0.973	0.979	8.948

13.3 Phase II Primary Endpoint

The study primary endpoint is progression free survival (PFS) rate at 1 year.

13.4 Secondary Endpoints

- The study secondary endpoints include: Overall response rate by RECIST or RECIST 1:1

- 1- year locoregional control (LRC), locoregional failure free survival (LFFS), distant metastasis (DM) and overall survival (OS) rates
- Acute and late toxicity accessed by the Common Terminology Criteria for Adverse Events (CTCAE)-5.0
- Fibrosis-related toxicities/functional outcomes
- Patient Reported Outcome (PRO) measures of symptoms using MD Anderson Symptom Inventory (MDASI).
- Volumetric tumor regression rate and MRI kinetic biomarkers after M7824 plus SBRT therapy
- Quality-Adjusted-Life-Years (QALY) between M7824 plus SBRT reirradiation and historic SBRT reirradiation control

13.5 Sample Size

The statistical considerations for the Phase I/II design are described as follows:

This is a phase I/II, open label, single arm study to evaluate M7824 plus SBRT in patients with locoregional recurrent HNSCC after prior head and neck radiotherapy that are not good candidates for salvage surgery (Figure 1). Patients must have evaluable disease by RECIST or RECIST 1:1 and a performance status ECOG 0-2. Time elapsed from prior radiotherapy must be at least 6 months.

Sample Size

In the phase I portion, 8 patients will be enrolled to access safety and toxicity. The primary endpoint is dose-limiting toxicity (DLT) defined as M7824 related \geq grade 3 adverse event (AE) unresolved to \leq grade 1 in \leq 28 days, or incomplete SBRT. DLT window is from first M7824 dose (D0) until 14 days post SBRT (D28). More than 2 DLTs in 8 evaluable patients will be considered unacceptable.

In the phase II portion, the primary endpoint is PFS at 1 year. Based on the prior studies [unpublished data from MD Anderson], we assume that the one-year PFS of the standard treatment is 0.60. If the new treatment improves the one-year PFS to 0.80 or higher, it will be considered a clinically important improvement. A sample size of 21 patients (with 1.5-year additional follow-up after the last patient is enrolled) will allow us to observe an improvement in 1-year PFS from 0.60 to 0.80. This will enable the study 80% power to detect the specified difference in PFS. Power was calculated using a log-rank test with a one-sided type 1 error rate of 0.10 (EAST 5.4 and STPLAN version 4.5). Based on our estimated accrual rate of 2 patients per month, we expect enrollment to be completed in 11 months. The total study duration is 29 months.

DMI (Data Management Initiative) database

Clinical data capture called DMI (Data Management Initiative) and CORe will be the electronic database used for this study's electronic case report forms.

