3. PATIENT ELIGIBILITY

3.1 Inclusion Criteria

Patients with histologically documented local-regional recurrent squamous cell carcinoma of the head and neck, or second primary squamous cell carcinoma of the head and neck;

Patients must be willing to undergo research biopsy for tissue collection at baseline and at disease progression;

Previous receipt of at least 30 Gy of radiation for HNSCC with overlapping fields;

Not eligible or poor candidate or patient refusal of surgery for recurrence;

Evaluable disease apparent on imaging (MRI or CT);

1 to 3 sites of recurrence (<60 cm³ per site, total volume <100 cm³);

Age ≥ 18 years;

Eastern Cooperative Oncology Group (ECOG) = 0, 1, or 2;

Adequate hematologic function defined as follows:

WBC ≥ 2000/µL;

Absolute neutrophil count (ANC) ≥ 1,500 cells/mm³;

Platelets ≥ 100,000 cells/mm³;

Hemoglobin ≥ 9.0 g/dl; Note: The use of transfusion or other intervention to achieve Hgb ≥ 9.0 g/dl is acceptable.

Adequate renal function as follows:

Serum creatinine ≤ 1.5 mg/dl or creatinine clearance (CC) ≥ 50 ml/min determined by 24-hour collection or estimated by Cockcroft-Gault formula:

$$\text{CCr male} = \frac{[(140 - \text{age}) \times (\text{wt in kg})]}{[(\text{Serum Cr mg/dl}) \times (72)]}$$

$$\text{CCr female} = 0.85 \times (\text{CrCl male}).$$

Adequate hepatic function as follows:

Total bilirubin ≤ 1.5 x ULN (except patients with Gilbert Syndrome who can have total bilirubin < 3.0 mg/dL);

AST or ALT ≤ 3 x the upper limit of normal.

Negative serum pregnancy test for women of childbearing potential and confirmation within 24 hours of first dose of study drug.

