- Grade 3, M7824 should be permanently discontinued for most of Grade 3 recurrent AEs, except for tumor flare phenomenon defined as local pain, irritation, or rash localized at sites of known or suspected tumor and clinically manageable Hgb decrease (< 8.0 g/dL).
- Grade 4, discontinue permanently, except for single laboratory values out of normal range that do not have clinical relevance.

Infusion-related Reactions Including Immediate Hypersensitivity

Infusion reaction may vary in manifestation and timing, and signs and symptoms usually develop during or shortly after drug infusion that generally resolve completely within 24 hours of completion of infusion. Infusion reactions like cytokine release syndrome may manifest similar signs and symptoms of immediate hypersensitivity/allergic reaction.

All study treatments will be administered on an outpatient basis. As a routine precaution, for the first 2 infusions, all participants enrolled in this study must be observed for 2 hours post end of infusion, in an area with resuscitation equipment and emergency agents. At all times during M7824 treatment, immediate emergency treatment of an IRR or a severe hypersensitivity reaction according to institutional standards must be assured. In order to treat possible hypersensitivity reactions like anaphylactic reactions, for instance, dexamethasone 10 mg and epinephrine in a 1:1000 dilution or equivalents, should always be available along with equipment for assisted ventilation. If no IRRs are observed during the first 2 infusions, the mandated 2 hours post infusion observation time may be reduced to 60 minutes.

Premedication with an antihistamine and with acetaminophen (eg, 25-50 mg diphenhydramine and 500-650 mg acetaminophen) approximately 30 to 60 minutes prior to each dose of M7824 is mandatory for the first 2 infusions, after which premedication is optional and at the discretion of the Investigator. Steroids as premedication are not permitted. If Grade ≥ 2 infusion reactions are seen during the first 2 infusions, premedication should not be stopped.

An assessment for possible IRR should be triggered based upon the development of specific symptoms within 24 hours of an infusion. These possible IRRs are identified based on a list of Medical Dictionary for Regulatory Activities (MedDRA) preferred terms (PTs) and criteria on the timely relationship to an infusion. IRRs are divided into reactions versus signs and symptoms.

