- Participants must enter the study with Hgb values at least 9 g/dL; routine blood test parameters are required in the Schedule of Assessments.
- All relevant hematologic testing for treatment-related anemias should be done prior to blood transfusion, if clinically feasible.
- If a participant experiences significant anemia (e.g., < 8 g/dL), then the amount of blood to be drawn may be reduced by not taking blood at selected time points for pharmacodynamic biomarkers. The decision to reduce the time points for these biomarkers will be taken by the Investigator in consultation with the Medical Monitor. This will be documented. Blood will continue to be taken as scheduled for safety analyses, PK, and anti-drug antibodies (ADAs).
- Transfusion should be performed at the discretion of the Investigator, based on clinical assessment and considered when participant experiences significant anemia. An attempt should be made to initiate work up (as specified below) for cause of anemia prior to transfusion if clinically feasible to not confound this work up. In general, blood transfusions and erythroid growth factors are permitted for Hgb \leq 7 g/dL and/or for life-threatening bleeding.

Guidance for evaluation of suspected treatment-related anemias is provided in

Table 3.

Discuss further management with the Medical Monitor for clinically significant treatment related- anemias.

Table 3 Evaluation Guidance of Suspected Treatment-related Anemia Adverse Events

Baseline Anemia Evaluation (Prior to Transfusion, if Feasible)	
Hb and CBC with differential (e.g., MCV, RDW, ANC, hematocrit, reticulocytes counts)	
Peripheral blood smear for cell morphological assessment	
Complete metabolic panel including liver panel-LFTs, bilirubin, LDH, renal function, and serum folate, B12 values and other chemistries:	

 • Coagulation factors (PT, PTT, INR) • Urinalysis • Iron panel (TIBC, ferritin, Fe) • TSH/hormonal panel • Fecal-occult blood testing • Erythropoietin. 	
Further Recommendation Based on Suspected Etiology (in Addition to Baseline Anemia Testing)	
Unknown etiology, suspect possible hemolysis	Coombs test, fibrinogen, haptoglobin, d-dimer Consider hematology consultation. Consider blood transfusion at clinical discretion.

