Unknown etiology, suspect possible bleeding	Consider blood transfusion at clinical discretion. Consider surgical/interventional radiology consultation. Consider imaging, as clinically indicated (e.g. FAST scan, CT scan, MRI, angiography). Consider endoscopy (upper/lower).
Unknown etiology despite above work-up	Hematology consultation. Consider bone marrow aspiration/morphologic evaluation.
ANC = absolute neutrophil count, Hgb = hemoglobin, CBC = complete blood count, INR = international normalized ratio, LDH = lactate dehydrogenase, LFT = liver function test, MCV = mean corpuscular volume, PT = prothrombin time, PTT = partial thromboplastin time, RDW = red cell distribution width, TIBC = total Iron binding capacity, and TSH = thyroid stimulating- hormone.	

Anemia severity reporting will follow the NCI-CTCAE v5 guidelines as below (

Table 4).

Table 4 Common Terminology Criteria for Adverse Events (CTCAE) Guidelines for Anemia Severity

CTCAE v.5	Grade 1	Grade 2	Grade 3	Grade 4
Anemia Hgb	Hgb < LLN-10.0 g/dL; < LLN-6.2 mmol/L; < LLN-100 g/L	Hgb < LLN-10.0-8g/dL; < LLN-6.2-4.9 mmol/L; < LLN-100-80 g/L	Hgb < LLN-8.0g/dL; < LLN-4.9 mmol/L; < LLN-80 g/L; transfusion indicated	Life-threatening consequences; urgent intervention indicated

Hgb = hemoglobin and LLN = lower limit of normal.
Signs and symptoms of anemia may include pallor of the skin and mucous membranes, shortness of breath, palpitations of the heart, soft systolic murmurs, lethargy, and fatigability.

Alterations in Wound Healing or Repair of Tissue Damage

Alterations of wound healing and tissue damage repair are considered a potential, theoretical risk for M7824 given TGF- β role in wound healing. Management should be discussed with the Medical Monitor for participants requiring surgery on study. Post-operative wound healing will be closely monitored.

Management should be discussed with the Supporting company EMD Serono for participants requiring surgery on study.

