10.2 Adverse Drug Reactions Requiring Treatment Modification

Clinical Laboratory Assessments

It is essential that the Supporting company EMD Serono or designee be provided with a list of laboratory normal ranges before shipment of study drug. Any change in laboratory normal ranges during the study will additionally be forwarded to the CRO and the Supporting company EMD Serono.

All routine laboratory analyses will be performed at a laboratory facility local to the study site, and relevant results must be available and checked before administration of treatment (details to be provided in the Laboratory Manual).

If a participant has a clinically significant abnormal laboratory test value that is not present at baseline, the test should be closely monitored until the test value has returned to the normal range or the Investigator has determined that the abnormality is chronic or stable.

The report of the results must be retained as a part of the participant's medical record or source documents.

Abnormal laboratory findings and other abnormal investigational findings (eg, on an ECG trace) should not be reported as AEs unless they are associated with clinical signs and symptoms, lead to treatment discontinuation, or are considered otherwise medically important by the Investigator. If a laboratory abnormality fulfills these criteria, the identified medical condition (eg, anemia, increased ALT) must be reported as the AE rather than the abnormal value itself.

See the Schedule of Assessments in Table 1 for further details.

Specific Planned Assessments or Adverse Events of Special Interest

AESIs are serious or non-serious AEs specific to known mechanism of action of the treatment drug that are of clinical interest requiring ongoing monitoring and rapid communication for optimal on-time management.

IRRs, including immediate hypersensitivity

Any signs or symptoms experienced by participants during the infusion or any event occurring during or within one day of drug administration should be evaluated as potential IRRs. IRRs are common ADRs with monoclonal antibodies (mAbs) timely related to drug administration and have been reported as anaphylaxis, anaphylactoid reactions and cytokine release syndrome, among other terms used. IRRs are an AESI for M7824, and important identified risks (adverse reactions) for M7824, the precautions and management are discussed in Section 0.

Immune-related adverse events (irAEs)

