If an ongoing SAE changes in its intensity or relationship to study drug or if new information becomes available, a follow-up SAE report should be sent within 24 hours to the EMD Serono (or designee) using the same procedure used for transmitting the initial SAE report.

All SAEs should be followed to resolution or stabilization.

The principal investigator will ensure that all SAEs in the clinical database are reported to EMD Serono and any applicable health authority during the conduct of the study.

SAEs will be reported on MDACC IRB approved form for prompt reporting (full form):

“Internal SAE Report Form for Prompt Reporting” Institutional Review Board.

SAEs will be submitted to both the Office of Protocol Research, Unit 1437 at The University of Texas MD Anderson Cancer Center and also sent to MEDWATCH

All SAEs should simultaneously be faxed or e-mailed to EMD Serono.

An SAE report should be completed for any event where doubt exists regarding its seriousness.

Definition of Dose Limiting Toxicity (DLT)

DLT for the combination of SBRT and M7824 in patients with recurrent HNSCC will be defined as:

1. Any \geq grade 3 AE resulting in inability to complete radiotherapy due to toxicity related to M7824 or the combination of M7824 and SBRT.

Drug destruction

Normal saline solution may be disposed of according to local site procedures. Other items used in the dose preparation and administration should be disposed of according to local site procedures.

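### Minor: under the Section 13.5 DLT wording, M7824-related grade 3 anemia that returns fully to an eligible entry hemoglobin of 9.0 to below 10.0 g/dL still counts as a DLT

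*Combined protocol and SAP*

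**What the plan says.** **The DLT rule.** Section 13.5 makes DLT the primary endpoint of the 8-patient phase I portion and defines it as "M7824 related \geq grade 3 adverse event (AE) unresolved to \leq grade 1 in \leq 28 days, or incomplete SBRT". More than 2 DLTs in 8 evaluable patients is unacceptable. Section 13.2 adds: "The phase 2 trial will proceed based upon the DLT data from the first 8 patients".

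**Entry hemoglobin.** Section 3.1 requires at least 9.0 g/dL and notes: "The use of transfusion or other intervention to achieve Hgb ≥ 9.0 g/dl is acceptable". The anemia guidance in Section 6.2.3 repeats the threshold: "Participants must enter the study with Hgb values at least 9 g/dL".

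**Grading.** In Table 4 (Section 6.2.3), grade 1 anemia ends at 10.0 g/dL, grade 2 is given as "Hgb < LLN-10.0-8g/dL", and grade 3 is below 8.0 g/dL or transfusion indicated.

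**Which laboratory changes are AEs.** Section 10.2 says that abnormal laboratory findings "should not be reported as AEs unless they are associated with clinical signs and symptoms, lead to treatment discontinuation", or the investigator otherwise considers them medically important.

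**A second DLT definition.** Section 12 counts an event of grade 3 or higher only if it is a "grade 3 AE resulting in inability to complete radiotherapy due to toxicity related to M7824 or the combination of M7824 and SBRT". It has no resolution test.

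**The concern.** The resolution target in 13.5 is an absolute grade, but eligible patients can start the trial above that grade. A patient who enters at 9.0 to below 10.0 g/dL is already at grade 2. After related grade 3 anemia, this patient must finish above the entry value to avoid being a DLT.

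Two invented cases show the effect:

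- Case A: entry 9.4, symptomatic fall to 7.8, back to 9.5 within two weeks. Recovery is complete, and 13.5 counts a DLT.
- Case B: entry 12.0, symptomatic fall to 7.8, 10.1 at 28 days. Recovery is (10.1 − 7.8)/(12.0 − 7.8) = 2.3/4.2 = 55% of the fall, and 13.5 counts no DLT.

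The point here concerns Case A only. Such an event is foreseeable. Treatment-related anemia is an adverse event of special interest for M7824, Section 2.5 lists anemia among the grade 3 or greater events seen, and a patient in this band reaches grade 3 after a fall of roughly 1 to 2 g/dL. What is at stake is one count in an endpoint where the third count makes the lead-in unacceptable.

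**Working it through.** **1. The texts side by side.**

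- Entry is allowed from 9.0 g/dL (Sections 3.1 and 6.2.3).
- Resolution under 13.5 means grade 1 or less, which for hemoglobin is 10.0 g/dL or above (Table 4).
- For entry values of 9.0 to below 10.0, full return to the entry value is therefore unresolved. None of the DLT wording in Sections 12, 13.2 or 13.5 gives a baseline exception.
- Sections 6.2.3 and 9.1 in general permit transfusion at 7 g/dL or below or for life-threatening bleeding, although 6.2.3 also leaves it to the investigator. A patient at 7.8 would not routinely be transfused up to 10.0.

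**2. The plan's own figures (Section 13.2).** With X binomial, n = 8, unacceptable if X ≥ 3:

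- DLT rate 0.50: P(X ≥ 3) = 1 − (1 + 8 + 28)/256 = 0.855 (stated 0.86).
- DLT rate 0.20: P(X ≤ 2) = 0.797 (stated 80%).

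Both reproduce.

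**3. Added DLT probability.** Let p be the DLT rate from all other causes. Let q be the probability that a patient enters at 9.0 to below 10.0 g/dL and has a reportable M7824-related grade 3 anemia that returns to the entry value but not to 10.0 within 28 days. Then q = share × risk, and the rate under 13.5 is 1 − (1 − p)(1 − q), taking the two sources as independent. Neither share nor risk is in the documents, so both are assumed.

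At p = 0.20:

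| Share | Risk in that group | q | P(X ≥ 3 of 8) | Shift (points) |
|---|---|---|---|---|
| none | none | 0 | 0.2031 | 0 |
| 10% | 0.5% | 0.0005 | 0.2040 | +0.1 |
| 10% | 1% | 0.001 | 0.2048 | +0.2 |
| 40% | 1% | 0.004 | 0.2102 | +0.7 |
| 40% | 2% | 0.008 | 0.2173 | +1.4 |
| 20% | 10% | 0.02 | 0.2393 | +3.6 |
| 30% | 20% | 0.06 | 0.3165 | +11.3 |

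The last two rows are stress cases. They are included because patients who start near 9 g/dL may carry a higher risk than average.

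For q = 0.001 to 0.004, the other DLT rates give:

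- p = 0.10: from 0.038 to 0.039–0.042.
- p = 0.30: from 0.448 to 0.450–0.455.

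**4. Chance of at least one such case in 8.** This is 1 − (1 − q)^8, which is 0.8% at q = 0.001 and 3.2% at q = 0.004.

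**5. If one such case occurs.** It moves the count from 2 to 3 only if exactly 2 of the other 7 patients have DLTs: C(7,2) p²(1 − p)⁵ = 0.124, 0.275 and 0.318 at p = 0.10, 0.20 and 0.30.

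**The case against.** **The error is conservative, and anemia is a named risk.** This stands. A strict absolute cut-off in a small safety cohort is a defensible choice, and Section 10.2 already removes asymptomatic falls that are not otherwise important. Relatedness must also be judged, and Section 6.2.3 notes that anemia has many causes in advanced cancer. These points limit the size. They do not explain why complete recovery should be called unresolved.

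**The size is not evidence from the documents.** This also stands. The only related-anemia rate given, 23 of 377 (6.1%), is for any grade and is not limited to 28 days, so it cannot serve as the risk. The figure of 1.4 points is a maximum only over the range chosen.

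**The case may not be a DLT at all.** Under the Section 12 definition, Case A does not count unless radiotherapy could not be completed. The documents do not settle which definition governs, so the point is conditional on 13.5.

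**Stronger readings that a reader might draw, and why they fail:**

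- *One such case would end the trial.* Under Section 13.2 a crossed boundary goes to the principal investigator and the supporting company for review, and Section 13.6 requires IND Office approval before phase 2. A third DLT leads to a decision, not to automatic closure.
- *The 20-patient monitoring is distorted too.* Section 13.2 does not say which DLT definition that monitoring uses.
- *Section 6.2.3 contradicts 13.5, because it exempts a "clinically manageable Hgb decrease (< 8.0 g/dL") from permanent discontinuation.* That exemption concerns stopping treatment for recurrent grade 3 reactions outside the ASCO guideline. An event can be exempt from discontinuation and still count as a DLT.

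**Conclusion.** The point holds as a minor defect of wording, on the condition that 13.5 is the governing DLT definition. In that case, full return to an eligible entry hemoglobin of 9.0 to below 10.0 g/dL after M7824-related grade 3 anemia is counted as a DLT. This follows from the text and needs no assumption.

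The direction is certain: DLTs are over-counted. The size cannot be derived from the documents. Under the assumed share of 10% to 40% and risk of 0.5% to 2%, the shift is about 0.1 to 1.4 points on the chance of an unacceptable lead-in at a DLT rate of 0.20. It would be larger if the subgroup's risk were well above that range. The review steps soften the consequence, but those reviewers would have no written rule for treating such a case as resolved, and would be deciding after seeing the count in an open-label study.

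**What to change.** Change Section 13.5 only. After the grade 1 resolution target, insert *or to baseline*, and define baseline as follows:

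- for laboratory AEs with a grade 2 baseline, the last value before the first M7824 dose;
- for other AEs, the baseline grade.

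The 28-day limit and the incomplete-SBRT clause stay as they are.

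For laboratory AEs the value is used because a grade rule would be too loose. A course of 9.9 to 7.9 to 8.0 recovers (8.0 − 7.9)/(9.9 − 7.9) = 5% of the fall, yet would be back at the baseline grade. For events such as pain or dysphagia there is no baseline value, so the grade is the workable reference.

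Add a listing of baseline, nadir and recovery hemoglobin, with transfusion dates, for each anemia event.

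**Cost.** One short insertion and one listing. Table 1 already has a CBC on days 1 and 15 of each cycle, and Section 9.1 already requires concomitant therapy to be recorded. There are three downsides. The DLT count becomes slightly less conservative for patients who enter at grade 2. Recovery to just below the entry value remains a DLT. A baseline reached by transfusion sets the target, which the listing would show.

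**What not to do here.** Do not copy this text into Section 12. That would drop the requirement there that failure to complete radiotherapy be due to related toxicity, and would add unresolved events in patients who completed SBRT. Which DLT definition governs is a separate and larger question and needs its own decision.

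### Sections 12 and 13.5 define DLT differently, and the printed end of the DLT window (D28) falls before 14 days after SBRT can have elapsed

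*Combined protocol and SAP*

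**What the plan says.** Section 12 (Adverse Events) closes with a headed definition of DLT. It has a single criterion: a "grade 3 AE resulting in inability to complete radiotherapy due to toxicity related to M7824 or the combination of M7824 and SBRT".

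Section 13.5 (Sample Size) gives another. "The primary endpoint is dose-limiting toxicity (DLT) defined as M7824 related" AEs of grade 3 or worse that have not come down to grade 1 or less within "28 days, or incomplete SBRT. DLT window is from first M7824 dose (D0) until 14 days post SBRT (D28"). The same paragraph carries the gate: "More than 2 DLTs in 8 evaluable patients will be considered unacceptable".

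Section 13.2 (Safety Lead-in) repeats the gate and adds Bayesian monitoring over the first 20 patients: "the patient enrollment will be halted if the numbers of observed DLTs exceed the following stopping rules", namely "at least 3 in 8, 4 in 9-11, 5 in 12-14, 6 in 15-17, and 7 in 18-20 patients". It says that the first of these looks is the 8-patient cohort already described. It does not define DLT, but it gives a window, which "is from first M7824 administration (D1) until 14 days post SBRT (D28").

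On timing, section 13.2 has M7824 "starting 2 weeks prior to the first fraction of SBRT". Section 6.1.3 gives SBRT as 5 fractions every other day over two weeks. Section 6.2.2 sets a 28-day cycle. Section 13.6 makes the lead-in toxicity summary due when eight evaluable patients have completed one cycle.

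**The concern.** A numerical safety rule should give one answer on one set of data, and this one need not. The two definitions classify the same patient differently, and no sentence says which governs. If section 12 were applied, a persistent severe M7824-related AE in a patient who completed all 5 fractions would not count towards the gate or any boundary. The plan also does not say whether SBRT left incomplete for a non-toxicity reason is a DLT or makes the patient non-evaluable.

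The window adds a second ambiguity. The lead-in objective (section 1.1) is the safety of M7824 given together with SBRT. If D28 is applied, most or all of the fortnight after the last fraction goes unobserved, and that is the period just after the combination has been delivered in full. The start day also differs: D1 in 13.2 and D0 in 13.5.

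**Working it through.** **The plan's own figures.** For the 8-patient gate, with X the number of DLTs:
- P(X ≥ 3 | n = 8, rate 0.5) = 0.855; the plan states 0.86.
- P(X ≤ 2 | n = 8, rate 0.2) = 0.797; the plan states 80%.

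With the Beta(0.3, 0.7) prior and the criterion P(rate > 0.3) > 0.6, all the printed boundaries are recovered. For example, the posterior probability is 0.638 at 3 of 8 and 0.340 at 2 of 8. The operating-characteristics table is recovered only with a maximum of 21 patients rather than the stated 20 (average N at rate 0.1 is 20.444 with 21 and 19.489 with 20). That does not bear on this point. The question here is which events and which days feed the rule.

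**Definitions side by side.**

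| Patient | Section 13.5 | Section 12 |
|---|---|---|
| M7824-related grade ≥3 AE, unresolved at 28 days, SBRT completed | DLT | not a DLT |
| Grade ≥3 AE related to M7824 or the combination, SBRT stopped because of it | DLT (incomplete SBRT) | DLT |
| SBRT stopped for a non-toxicity reason | DLT if read literally | not a DLT |

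In a constructed extreme, 3 of 8 patients have the first pattern and no other events occur. They score 3/8 under 13.5, which fails the gate, and 0/8 under section 12.

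**Sensitivity, on an assumption.** The documents give no rate for either definition. Suppose the 13.5 DLT rate is 50% and section 12 captures 100, 75, 50 or 25% of those events. Then P(X ≥ 3 of 8) is 0.855, 0.630, 0.321 or 0.067. This shows that the rule depends on the definition; it is not an estimate. The nearest figure in the documents is in section 2.5: 58/377 = 15.4% with a grade 3 or worse AE in the M7824 expansion cohorts, or 8 × 0.154 = 1.2 expected in 8 patients. It is not limited to the DLT window or to unresolved events, and it is without SBRT, so it is not a DLT rate.

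**Window.** The first fraction falls 14 days after the first dose. Five fractions strictly every other day put the last one 8 days after the first; using the full two weeks puts it 13 to 14 days after.

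| First dose labelled | First fraction | Last fraction | Last fraction + 14 | First fraction + 14 |
|---|---|---|---|---|
| D0 (13.5) | D14 | D22 to D27 or D28 | D36 to D41 or D42 | D28 |
| D1 (13.2) | D15 | D23 to D28 or D29 | D37 to D42 or D43 | D29 |

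So 14 days after SBRT is about D36 to D42, which is 36 − 28 = 8 to 42 − 28 = 14 days beyond the printed D28. A D28 cut-off leaves 28 − 22 = 6 down to 28 − 28 = 0 days after the last fraction.

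**Resolution period.** Failure to resolve over 28 days cannot be judged by D28 for any AE that starts after D0. Under 13.5 some patients therefore cannot be classified when the end-of-cycle-1 summary falls due.

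**The case against.** The best case on the other side is that 13.5 prints its definition and the gate in one paragraph and calls it the primary endpoint, so a statistician would use it, and section 12 is a single stray sentence. That stands as a reading. It does not remove the conflict, because section 12 is the headed definition in the section on adverse events.

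A reader might infer that the Bayesian boundaries rest on no definition at all. The documents do not support that. Section 13.2 makes the 8-patient gate the first Bayesian look, and its first boundary, 3 in 8, is the same rule. If 13.5 governs the gate, it naturally carries through to patient 20.

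A reader might also infer that section 12 is simply the narrower text. On attribution it may be wider, since it includes toxicity of the combination, while the AE limb of 13.5 names M7824 alone. Copying 13.5 unchanged into section 12 would lose that.

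On the window, D28 is printed twice. It is 14 days after SBRT start on the D0 count, and it matches the end of cycle 1. It may be the intended cut-off, but the words say otherwise in both places.

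Finally, the rule is not the only protection. SAEs go to the IND Office, IND Office approval is needed before phase 2, phase II toxicity summaries follow every 3 evaluable patients, and section 8.3 allows the trial to be stopped. Crossing a boundary halts enrolment for review and does not by itself end the trial. All of this stands, but none of it tells anyone which patients to count.

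**Conclusion.** The concern holds. Two conflicting definitions of the lead-in primary endpoint stand in the same document, with 13.5 the natural one to apply and section 12 the text to bring into line. The stated end of the DLT window contradicts the treatment schedule by about 8 to 14 days.

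The window result rests on the first fraction being given 14 days after the first dose and the last fraction 8 to 14 days after that. The conflict between definitions rests on the wording alone. Its effect on the probability of stopping cannot be sized from the documents, and the 3/8 against 0/8 example is an extreme chosen to show the mechanism.

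It would go too far to say that the gate probabilities or the boundaries are miscalculated, since they reproduce, or that patients would be unprotected. The defect is that a numerical safety rule can return two answers on the same data. It should be corrected because the count decides entry to phase 2 and the correction is cheap.

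**What to change.** Put one definition in sections 12, 13.2 and 13.5: a grade 3 or worse AE related to M7824 or to the combination of M7824 and SBRT that has not resolved to grade 1 or less within 28 days, or SBRT not completed because of such toxicity. State that a patient whose SBRT is incomplete for a non-toxicity reason is not DLT-evaluable. Say also how a stop for toxicity attributed to SBRT alone is scored, since the wording above does not settle it.

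State one window, from the first M7824 dose (one day label) to 14 days after the last SBRT fraction, about D36 to D42. Take the phase 2 decision only when all 8 patients have completed that window and any open 28-day resolution period.

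I would not extend this waiting requirement to each Bayesian look at patients 9 to 20. DLTs would enter the count as they occur while patients without one would enter late, which could push interim counts upward. It would also slow accrual: at the planned 2 patients per month, a wait of 42 to 70 days leaves about 2 × 42/30.4 = 2.8 to 2 × 70/30.4 = 4.6 enrolled patients pending at a look.

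The cost is a wording amendment and a later phase 2 decision: 8 to 14 days after D28 if no related severe AE is open, and up to D42 + 28 = D70, or 42 days (about 6 weeks), if one is.
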